**Laboratory evaluation:**

The following laboratory parameters will be evaluated:

1. Hematology – Hemoglobin, hematocrit, red blood cell (RBC) count, white blood cell (WBC) count, platelet count, and differential blood count (only if indicated)
2. Biochemistry -

Random blood sugar, liver function tests [ serum bilirubin, alkaline phosphatase, ALT (alanine amino transferase), AST (aspartate amino transferase), LDH (lactate dehydrogenase), gamma-glutamyl transferase], calcium, potassium, Serum Prolactin (Fasting), Serum Lipase (only baseline)

For all laboratory parameters with values outside the normal range (or abnormal results), the clinical significance will be judged by the Investigator.

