### **16.3 Appendix –Clinical laboratory(ies) involved in the trial**

The respective local clinical laboratories will be used after site selection.

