#### Laboratory Data:

Laboratory variables for hematology and biochemistry, including changes from baseline will be summarized. A frequency table will be presented for markedly abnormal values. Markedly abnormality for hematology will be determined based on the standard criteria outlined in Table 3 of SAP module 2. Markedly abnormality for Biochemistry variables will be determined based on the standard criteria outlined in Table 2.

The criteria for non-specified variables are as follows:

Variable	SI Units		
	Unit	Lower Limit	Upper Limit
Random Blood Sugar	mmol/L	3.9	11.1
Serum Prolactin	mcg/L	--	0.1 (100ng/l)
Serum Lipase	U/L	--	420
Ionized Calcium	mmol/L	0.9	1.5

Blood differentials whose values are reported in %, the limits for markedly abnormal values that are as follows:

Variable	SI Units		
	Unit	Lower Limit	Upper Limit
Basophils	%	--	4
Eosinophils	%	--	5
Lymphocytes	%	--	40
Monocytes	%	--	10
Neutrophils	%	--	70

Shift tables will be presented according to the lab reference ranges (low, normal, or high). Refer section 3.6.2 of SAP Module 2 for detailed analysis strategy.

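### The markedly abnormal limits for differentials reported in % are upper-only, so a low neutrophil or lymphocyte percentage cannot be counted as markedly low in the hematology incidence table.

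*SAP*

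**What the plan says.** SAP 4.3, Laboratory Data, plans a frequency table of markedly abnormal values. For hematology the criteria are in another document: "Markedly abnormality for hematology will be determined based on the standard criteria outlined in Table 3 of SAP module 2". The section then gives study-specific limits for some chemistry variables and, separately, for differentials in percent: "Blood differentials whose values are reported in %, the limits for markedly abnormal values that are as follows". Two rows of that second table read "Neutrophils % -- 70" and "Lymphocytes % -- 40". The other three rows have the same form, with upper limits of 4 for basophils, 5 for eosinophils and 10 for monocytes. The chemistry table just above uses the same columns and does fill in lower limits where they are wanted, for example "Ionized Calcium mmol/L 0.9 1.5".

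The section also says: "Shift tables will be presented according to the lab reference ranges (low, normal, or high". SAP 9.3 lists the outputs: LBT004 (incidence of markedly abnormal hematology), LBT003 (shifts) and LBL008 (a listing of values that are markedly abnormal or judged clinically significant).

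On data collection, the hematology panel in Protocol 8.2 includes "white blood cell (WBC) count, platelet count, and differential blood count (only if indicated"). Hematology is scheduled at V1 and V4 (Protocol 8.6, Table 2). On laboratories, Protocol 16.3 says: "The respective local clinical laboratories will be used after site selection".

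**The concern.** A markedly abnormal criterion is meant to pick out extreme values. For white-cell differentials, both directions can matter in a safety review. With an upper limit only, the incidence table cannot record a low neutrophil or lymphocyte percentage as a low finding, however extreme it is. A reader who sees zero markedly low neutrophils in LBT004 could take this as evidence that none occurred, when the rule makes any other count impossible for results in percent.

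The reporting unit also decides which criteria apply: percentages go to this table, and other hematology results go to Module 2 Table 3. With local laboratories, the unit may depend on the site.

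**Working it through.** The plan states no figure to reproduce, so the check applies the stated limits directly.

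**Is the dash an extraction gap?** No. Random blood sugar (3.9) and ionized calcium (0.9) have lower limits in the table above, in the same layout. The dash in the differential table therefore means that no lower limit is set. SAP 7.2, item 7, records that this SAP version defined the ranges for non-standard hematology and biochemistry variables, so they can be corrected here.

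**Inputs.** Upper limits in % (SAP 4.3): basophils 4, eosinophils 5, lymphocytes 40, monocytes 10, neutrophils 70. Assumptions: a value is flagged if it exceeds its upper limit, and the five cell types sum to 100%.

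**Step 1. Direct reading.** With no lower limit, a neutrophil or lymphocyte value anywhere from 0% up to its upper limit raises no flag for that cell type.

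**Step 2. How low can a cell type go with no differential flag at all?** The lowest such value is 100 minus the sum of the other four upper limits. All five limits sum to 4 + 5 + 40 + 10 + 70 = 129.
- Neutrophils: 100 − (4 + 5 + 40 + 10) = 100 − 59 = 41%.
- Lymphocytes: 100 − (4 + 5 + 10 + 70) = 100 − 89 = 11%.

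**Step 3. Example differentials.**

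| Neutrophils | Lymphocytes | Monocytes | Eosinophils | Basophils | Sum | Flag raised |
|---|---|---|---|---|---|---|
| 70 | 11 | 10 | 5 | 4 | 100 | none |
| 41 | 40 | 10 | 5 | 4 | 100 | none |
| 1 | 85 | 10 | 3 | 1 | 100 | lymphocytes high |

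In the third row the subject does enter LBT004, but as high lymphocytes. The neutrophil value of 1% is not counted.

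**Step 4. Percentages and absolute counts.** Absolute count = % × WBC / 100. The documents give no WBC values, so 4.0 and 6.0 ×10^9/L are assumed for illustration.
- Lymphocytes 11%: 4.0 × 0.11 = 0.44 and 6.0 × 0.11 = 0.66 ×10^9/L. Neither is flagged for lymphocytes.
- Lymphocytes 41%: 4.0 × 0.41 = 1.64 and 6.0 × 0.41 = 2.46 ×10^9/L. Both are flagged.

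The documents give no reference ranges, so no clinical reading is attached to these counts. They show only that the percent rule flags the larger counts and passes over the smaller ones.

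**The case against.** The strongest reply is that a low value is not lost from the study report. Shift tables classify results as low, normal or high. LBL008 takes in values judged clinically significant, and Protocol 8.2 has the investigator judge every value outside the normal range. An abnormal laboratory finding can be an adverse event (Protocol 9.1), and quantitative hematology is summarised with change from baseline. A reader might infer from the one-sided limits that a low result can never be flagged anywhere. The documents do not support that: the gap is in the markedly abnormal criterion for that cell type. By the arithmetic above, a subject with 10% neutrophils must also appear in LBT004 under some other cell type, because the remaining 90% exceeds the 59% that the other four limits allow. All of this stands. It does not repair LBT004: the shift tables do not grade how low a value is, LBL008 is a listing that depends on individual judgement, and a high flag on another cell type reports the wrong direction.

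A second reply concerns sites. A reader might infer that subjects at sites reporting in other units would be flagged when low, so that sites are treated unequally. Module 2 Table 3 is not among the documents. Whether it has differential rows, uses absolute counts or sets lower limits could not be checked, and the documents do not say which laboratories report in percent. What is shown is only that percentages follow a different set of criteria from Table 3.

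Third, the stakes are small. The differential is done only if indicated, hematology is scheduled at two visits, and LBT004 is descriptive. Central 1:1 randomization (Protocol 4.1 and 7.4) gives no reason to expect the reporting unit to differ systematically by arm. This stands and sets the severity.

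**Conclusion.** The limits are wrong as written, but the matter is minor. For differentials reported in %, a low neutrophil or lymphocyte value cannot be counted as markedly low for that cell type in LBT004. This follows from the table alone. The further result, that values down to 41% (neutrophils) or 11% (lymphocytes) can pass with no differential flag and that lower values surface only as a high flag elsewhere, assumes that the five cell types sum to 100% and that a flag requires exceeding the limit.

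The number of subjects affected is unknown: the documents give neither how often a differential will be done nor how many laboratories report in percent. The effect is limited to descriptive safety output; the primary efficacy conclusion is untouched. Unequal treatment of low values between sites is possible but not shown, because it depends on Module 2 Table 3.

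**What to change.** First check Module 2 Table 3, then revise the differential limits in SAP 4.3.

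- If Table 3 holds two-sided absolute-count limits for these cells: where a same-sample WBC is available, derive absolute count = % × WBC / 100 and apply the Table 3 limits. WBC is in the same hematology panel, so no new data are needed. If WBC is missing, list the percentage without a markedly abnormal flag.
- If it does not: add lower limits, with the sponsor's justification, for at least neutrophils and lymphocytes to the % table, and check that they are consistent with Table 3.

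The cost is one SAP sentence and one extra derivation, or a few added table entries with their justification.

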#### Vital Signs:

Vitals signs, including changes from baseline will be summarized. A frequency table will be presented for markedly abnormal values. Markedly abnormal will be determined based on the standard criteria outlined in Table 5 of SAP module 2. Listing VSL005 will include an additional column to present local lab reference ranges, if required. Refer section 3.6.3 of SAP module 2 for detailed analysis strategy of vital signs.

Additional safety laboratory data, if captured, will be presented in by-subject data listings.

#### Other analysis

Only the necessary tables as required for the study will be generated, as specified in section 9.3, which provides the list of required reports.

The assignment of subjects to subject samples, the disposition of subjects with respect to premature termination, reason for premature termination, protocol deviations will be summarized per treatment group as per section 3.1, 3.2 and 3.3 of SAP module 2.

Demographics and other baseline characteristics will be summarized per treatment group as per section 3.4.1 and 3.4.2 of SAP module 2.

Medical history, including coding data will be summarized per primary SOC, per HLT by primary SOC and per PT by HLT and primary SOC as per section 3.4.3 of SAP module 2.

Concomitant medication, including coding data will be summarized per assigned treatment period for incidence per subject, for primary therapeutic subgroup (3rd level ATC code) and for generic name by therapeutic subgroup as per section 3.5 of SAP module 2.

Rescue Medications will be presented in by-subject data listings only. Any impact on safety or efficacy endpoints will be evaluated after final BDR and the analysis strategy will be provided.

Drug exposure and treatment compliance will be summarized per treatment group. Refer [section 5.5](#) of SAP module 1.

Additional data, if captured at screening, will be presented in by-subject data listings.

#### 4.4 Interim Analysis

No interim analysis has been planned for this study.

#### 4.5 Data Safety Monitoring Board

Not applicable.

#### **4.6 Safety Management Team**

Not applicable.

#### **4.7 Subgroup Analysis**

Primary, secondary efficacy endpoints (LDQ at 4 and 8 weeks, NRS11 (different symptoms), responder rate, functional dyspepsia score by SF-NDI, raw and transformed scores by SF NDI), exploratory endpoint of treatment acceptance and safety endpoints (overall summary of AEs, prolactin levels and change from baseline in prolactin) will be analyzed across subgroups using the same analysis as specified for the primary, secondary and safety endpoints.

The subgroups are defined as follows:

Gender:

- Female
- Male

Age Group:

- $\geq 18$  to  $\leq 44$
- $\geq 45$  to  $\leq 59$
- $\geq 60$

Geographical region (Country):

- Armenia
- Malaysia
- Philippines
- Thailand
- Vietnam

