## **Efficacy**

### Primary efficacy:

- An ANCOVA analysis will be performed with the change in the LDQ score as dependent variable and treatment group, site and LDQ baseline value as additional factors. The difference between the two treatment groups will be calculated for the non-inferiority comparisons, together with a two-sided 95% confidence interval. Non-inferiority will be considered achieved if the lower bound of the 95% confidence interval of the difference

---

between the two groups is greater than 1.75 (NI-margin). Normal approximation will be assumed for the parametric analyses. The primary analysis will be performed for both the per protocol set and the full analysis set. The analysis for the per-protocol set will be regarded as primary.

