#### **10.5 Subgroup Analysis**

Subgroup analyses by geographical regions will be performed. Key efficacy and safety results will be summarized across subgroups defined by geographical regions (country, gender and age).

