#### **10.7 Determination of Sample Size**

Assumptions for sample size calculation are based on the studies of Holtmann et al. and Talley et al. from which a standard deviation of 7 can be assumed for the change of the LD questionnaire.

For the NI margin following assumptions were made:

- In the Holtmann study a difference to placebo 2 (95% CI: 0.03-3.97) in the LDQ was reported.
- In the Ang publication (2011) a difference of 10-15% to placebo is regarded as clinically relevant
- NI-margin needs to be lower than 2. A difference of 15% results in 1.74. Therefore, a NI margin of 1.75 is chosen.

---

Assuming a NI margin of 1.75 and standard deviation of 7 for the change in the LDQ severity score, 253 subjects per treatment arm are required to conclude non-inferiority between the 2 treatment groups with a power of 80% at  $\alpha$ -level of 2.5% single sided. Adding a 10% drop-out rate the total sample size would be 564 subjects (N= 282 per arm).

---

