**Table 10.1.2.1.1.2: Change in Leeds Dyspepsia Questionnaire (LDQ) Severity Score at week 8 (by Gender)**

PER PROTOCOL SUBJECT SAMPLE

Gender Visit	Statistics	
 (N=xxx)	
 (N=xxx)
Male,	n	xx	xx
Baseline	n	xxx	xxx
	Mean (SD)	xx.x (x.x)	xx.x (x.x)
	Median	xx.x	xx.x
	Min/Max	xx/xx	xx/xx
Week 8	n	xxx	xxx
	Mean (SD)	xx.x (x.x)	xx.x (x.x)
	Median	xx.x	xx.x
	Min/Max	xx/xx	xx/xx
Change from Baseline at Week 8	n	xxx	xxx
	Mean (SD)	xx.x (x.x)	xx.x (x.x)
	Median	xx.x	xx.x
	Min/Max	xx/xx	xx/xx
	LS Mean (SE)	xx.x (x.x)	xx.x (x.x)
	95% CI for LS Mean	xx.x, xx.x	xx.x, xx.x
	LS Mean difference (SE)	xx.x (x.x)	

95% CI for LS Mean difference    xx.x, xx.x  
p-value                                x.xxx

Note 1: Baseline is defined as the last available observation prior to the first study drug administration.

Note 2: LS Mean, LS Mean difference, SE, 95% CI and p-value is calculated by using the analysis of covariance (ANCOVA) model includes change in the LDQ score as dependent variable and treatment group, site and LDQ baseline value as covariates.

Source: LXX00X.sas, <CRO>.Run DDMMYYYY HH:MM  
Abbott Protocol CCCC-xxx-yyyy

Page x/y

*Remark (not part of the table):*

*Repeat similar table for*

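### Subgroup tables repeat the primary ANCOVA and its zero-difference p-value inside each gender, age and country level with no treatment-by-subgroup term, so they do not address whether the formulation difference varies between subgroups

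*SAP*

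**What the plan says.** Protocol 10.5 announces subgroup analyses by geographical region and adds: "Key efficacy and safety results will be summarized across subgroups defined by geographical regions (country, gender and age". It names no method.

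SAP 4.7 supplies one. The listed endpoints "will be analyzed across subgroups using the same analysis as specified for the primary, secondary and safety endpoints". The levels are female and male; three age bands; and Armenia, Malaysia, Philippines, Thailand and Vietnam.

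The primary model in SAP 4.2.1 regresses LDQ change on baseline score, treatment and site. Its sample code requests the LS-mean difference with the default p-value, which tests a difference of zero.

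The by-gender shell, Table 10.1.2.1.1.2, has rows for the LS-mean difference, its confidence interval and a p-value within each level. Its note says "LS Mean, LS Mean difference, SE, 95% CI and p-value is calculated by using the analysis of covariance (ANCOVA) model". The age and country tables repeat that layout, as do the full-analysis versions (Tables 10.1.2.1.2.2 to 10.1.2.1.2.4). SAP 9.3.1 marks those three full-analysis tables as headline results; the per-protocol subgroup tables are not marked.

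The only interaction with treatment in either document is treatment by visit in the MMRM sensitivity analysis. SAP 9.3.3 lists two flowcharts and no forest plot.

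**The concern.** The useful question for a subgroup table in a five-country trial is whether the formulation difference changes from one level to another. A set of separate tests against zero does not ask that question. A non-significant p-value in one country is not evidence that the formulations are alike there. One significant country beside four non-significant ones is not evidence that countries differ. Both patterns depend heavily on how many subjects each level contains.

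The full-analysis LDQ subgroup tables are headline output, so they are likely to be read level by level, and the SAP gives no rule for interpreting their p-values. What is at stake is the reading of secondary output, not the primary conclusion.

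**Working it through.** **Inputs.** From Protocol 10.7: 80% power; an alpha "level of 2.5% single sided"; 10% drop-out; a required evaluable number of 253 per arm; and, for the margin and spread, "Assuming a NI margin of 1.75 and standard deviation of 7 for the change in the LDQ severity score". From the protocol's primary efficacy paragraph: the difference is given "together with a two-sided 95% confidence interval". Not in the documents, so assumed: the share of subjects in each level, SD 7 in every level, and no variance reduction from baseline or site adjustment.

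**The plan's own figure.** n per arm = 2 × (1.96 + 0.8416)² × 7² / 1.75² = 2 × 7.849 × 16 = 251.2, so 252 by the normal approximation. The noncentral t gives power 79.98% at 252 and 80.14% at 253, which reproduces 253. Then 253 / 0.9 = 281.1, so 282 per arm and 564 in total.

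**Within-level precision.** SE = 7 × √(2/n), with n the evaluable subjects per arm in the level. For five equal countries n = 253 / 5 = 50.6, SE = 1.39, and the 95% half-width is 1.96 × 1.39 = 2.73.

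**Chance of a non-significant p-value when a true deficit exists.** Power is Φ(d/SE − 1.96) plus a negligible opposite tail. For d = 1.75 and n = 50.6, power is 0.242, so 76% of such results are non-significant. Over a range of sizes:

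| Level (assumed share) | n per arm | SE | Half-width | Non-significant, d = 1.75 | Non-significant, d = 3.5 |
|---|---|---|---|---|---|
| Country, 40% | 101.2 | 0.98 | 1.93 | 57% | 6% |
| Country, 20% | 50.6 | 1.39 | 2.73 | 76% | 29% |
| Country, 10% | 25.3 | 1.97 | 3.86 | 86% | 57% |
| Country, 5% | 12.7 | 2.78 | 5.46 | 90% | 76% |
| Age, one third | 84.3 | 1.08 | 2.11 | 63% | 10% |
| Gender, one half | 126.5 | 0.88 | 1.73 | 49% | 2% |

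**Chance findings.** With no true difference anywhere, P(at least one of five country p-values < 0.05) = 1 − 0.95⁵ = 0.226. For all ten levels, 1 − 0.95¹⁰ = 0.40; this is somewhat too high because the three factors classify the same subjects.

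**What an interaction term would deliver on 253 per arm.** For a contrast between two groups, SE = 7 × √(2/n₁ + 2/n₂).

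- Gender, 50/50: SE 1.24, half-width 2.44. Power is 29% if the effects differ by 1.75 points and 80% if they differ by 3.5.
- One country of five against the rest: SE 1.56, half-width 3.05. Power is 20% and 61%.
- Global country test on 4 df, one country deviating: the variance of each country's difference is 2 × 49 / 50.6 = 1.94, and the noncentrality is 0.8 × d² / 1.94. Power is 12% for 1.75 points and 40% for 3.5.

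**The case against.** The strongest reply is that this is descriptive output and no decision depends on it. Neither document says that the subgroup tables test consistency, or that a non-significant p-value means comparability. That stands, and it limits the weight of the point.

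A reader might infer that SAP 4.7, by calling for the same analysis, carries the 1.75 non-inferiority rule into every country, where it would often be missed for lack of subjects. The documents do not support that reading. SAP 4.2.1 assesses non-inferiority in the study population as a whole and ties study success to that result. The subgroup shells have no margin row and no verdict row. The wording of 4.7 leaves a small ambiguity that a cross-reference would close.

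A reader might also infer that within-country p-values would mostly be non-significant whatever the deficit. With five equal countries that is true at 1.75 points but not at 3.5, which would be detected about 71% of the time. Nor is running analyses by country a departure from the protocol, since Protocol 10.5 announces them.

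Finally, the shells already give a difference and interval per level, and an interaction test has little power. Both are true. The gain is that the interaction estimate and its interval bear directly on whether the effect varies, which no set of within-level p-values does.

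**Conclusion.** The point holds as a cheap improvement that the sponsor should consider. The planned subgroup output does not address whether the formulation difference varies by gender, age or country, and its p-values invite readings that they cannot bear. The primary test, its type I error and the success criterion are untouched.

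The headline sizes (half-width about 2.7 points, 76% non-significant at a 1.75-point deficit, 23% chance of a false signal in at least one country) rest on five equal countries, SD 7 and about 51 evaluable subjects per arm per country. Unequal enrolment would worsen the first two in the smaller countries and ease them in the larger ones. Variance reduction from covariate adjustment would narrow all the intervals. The 23% depends only on five independent tests at 5%.

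**What to change.** In SAP 4.7, replace the separate within-level LDQ ANCOVAs by one model per factor, fitted to all subjects in the analysis sample concerned: change on baseline, treatment, site, subgroup and treatment × subgroup. For country, omit the main effect, because sites nest within countries. Then:

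- report the treatment difference with its 95% confidence interval for each level, ideally as a forest plot, and the interaction estimate or test, all labelled descriptive;
- remove the p-value rows from the subgroup shells, including those for quality of life, NRS 11, responders, treatment acceptance and prolactin;
- in the country table, drop the per-arm LS-mean rows or compute them with country-specific site weights. With site fixed and nested in country they are non-estimable by default, although the treatment differences remain estimable;
- add a cross-reference to SAP 4.2.1 stating that the 1.75 rule applies to the overall study population only.

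The cost is SAP wording, one model term and edited shells, with no new data. The downside is the low power of the interaction test (about 12% for one country deviating by 1.75 points and 29% for gender), so the SAP should state that a non-significant interaction does not show consistency.
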